  13. If an index tumor is amenable for excisional biopsy at Cycle 1 Day 1, then excisional biopsy may be performed at the discretion of the investigator. In this case, a separate index tumor will be identified for subsequent research biopsies.
  14. Cryoablation is performed on Day 8 of Cycle 2 only. If the previously identified tumor for cryoablation is decreased in size and can no longer be cryoablated, another tumor amenable to cryoablation will be identified for treatment. If no additional tumors can be identified for cryoablation, DC will be injected into the previously identified shrinking tumor.
  15. LDH performed on Day 1 of Cycles 4, 8, 12, and 18.
  16. After Cycle 10, responsive or stable patients can be followed every other cycle by treating physician/provider until last cycle of treatment. However, patients will be followed by nurse at each cycle of treatment for adverse event assessment. They will be seen as needed by provider.
  17. If subject thyroid function tests are within normal at the end of treatment and have no clinical signs and symptoms of thyroiditis, thyroid function test does not need to be performed during active monitoring. If thyroid function tests are abnormal during treatment, these tests need to be followed until they return to normal.
  18. Retreatment starts at cycle 2.
  19. Every 3 months.
- R Research funded.

**4.3 Test Schedule for Observation for patients who do not complete initial active treatment for any reason or do not have dendritic cells for retreatment.**

	Active Monitoring	
	Observation 	
	Day 1 of each observation cycle Every 3 months for 1 year (start at Week 62 or 8 weeks after last dose whichever is earlier)	Documented PD at any time during this protocol treatment or observation, prior to entering event monitoring, at End of Observation
Tests and procedures		
Physical exam and PS	X	X
Serum pregnancy test		
Pembrolizumab (MK-3475) administration R		
Cryoablation R		
Leukapheresis and DC manufacturing R		
Cellular Vaccine (DC) administration R		
Prevnar administration		
Chemistry Profile (Creatinine, TBili, AST, ALT, Alk Phos)	X	X
Thyroid function cascade	X 	
LDH	X	X
Coagulation (INR)		
Hematology (ALC, WBC with differential, Hgb, PLT)	X	X
Adverse Event Assessment	X	X
Radiologic evaluations (CT whole body, or PET/CT)	X	X
Research blood for Immune Monitoring R	X	X

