#### 4.5 Test Schedule for Treatment Observation for patients who have dendritic cells for retreatment

	Treatment Observation		
	Day 1 of each cycle Every 3 months for 1 year post treatment(start at Week 62 or 8 weeks after last dose whichever is earlier)	Day 1 of each cycle (Every 4 months during second year post treatment, every 6 months thereafter until 4 yr post registration)	Documented PD at any time during treatment or observation, prior to entering event monitoring, at End of Observation
Tests and procedures			
Physical exam and PS	X		X
Serum pregnancy test			
Pembrolizumab (MK-3475) administration R			
Cryoablation R			
Leukapheresis and DC manufacturing R			
Cellular Vaccine (DC) administration R			
Pevnar administration			
Chemistry Profile (Creatinine, TBili, AST, ALT, Alk Phos)	X		X
Thyroid function cascade	X 		
LDH	X		X
Coagulation (INR)			
Hematology (ALC, WBC with differential, Hgb, PLT)	X		X
Adverse Event Assessment	X		X
Radiologic evaluations (CT whole body, or PET/CT)	X		X
Research blood for Immune Monitoring R	X		X
Tumor biopsies 1, R	X 		X 
FACT-Lym	X		X

	Treatment Observation		
	Day 1 of each cycle Every 3 months for 1 year post treatment(start at Week 62 or 8 weeks after last dose whichever is earlier)	Day 1 of each cycle (Every 4 months during second year post treatment, every 6 months thereafter until 4 yr post registration)	Documented PD at any time during treatment or observation, prior to entering event monitoring, at End of Observation
Tests and procedures			
Event Monitoring Form*		X	

\* Also complete at PD, every 6 months post PD until 4 yr post registration, death and at each new occurrence of primary up to 4 years post registration. If a patient is still alive 4 years after registration, no further follow-up is required. Submit copy of documentation of response or progression in the Supporting Documentation form in Medidata Rave.

1. An index tumor for biopsy is identified as accessible via needle biopsy that is not the cryoablation site.

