#### 7.113 Pembrolizumab, monoclonal anti-PD1 antibody

Patients will receive pembrolizumab at 200 mg IV every 3 weeks for 18 cycles. If patient experienced adverse events requiring dosing delay (see Section 8), the new dosing interval (increased interval) can be defined as the new cycle length. Patients who achieved CR before Cycle 5 will complete treatments through cycle 6 and can then stop treatment at the discretion of the treating provider and investigators. Patients who achieved CR at or after cycle 5 could continue treatments for 2 more cycles and stop treatment at the discretion of the treating provider. The designed maximum length of treatment is 12 months (365 days). If the patient is continuing to benefit from treatment after 12 months, the patient may continue to receive treatment up to 24 months at investigator/sponsor discretion.

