### 13.3 Treatment Observation

- 13.31 If the patient has achieved CR, PR, or SD in initial treatment or optional pembrolizumab cycles, not requiring non-protocol alternative treatment, the patient will be observed at the following time points: 8 weeks after the last dose of treatment and then every 3 months for 1 year; followed by monitoring every 4 months for a year, then every 6 months until 4 years post registration.

During Treatment Observation , the patient may be retreated at any time

following PD (see Section 13.8).

- 13.4 Patients who complete Treatment Observation without PD will have completed the study 4 years post registration.
- 13.5 Patients who develop PD during initial active treatment in the DC + Pembrolizumab cycles, will go to the event-monitoring phase(see Section 4.4).
- 13.6 Patients who develop PD during initial active treatment receiving only Pembrolizumab (cycles 6+ on dose level 1 or cycles 8+ on dose level -1) will go to observation (see Section 4.4) or retreatment per clinical judgment.
- 13.7 Patients who develop PD during the optional Pembrolizumab treatment will:
- Go to retreatment if DC is available
  - Go to observation (see Section 4.3) if DC unavailable or if the patient refuses further treatment or if the clinician determines retreatment isn't feasible.
- 13.8 Patients who develop PD during the observation phase with no DC available for retreatment, will go to event monitoring (see Section 4.4).
- 13.9a Patients who develop PD during the treatment observation phase who have DC available will:
- Go to retreatment (see Section 13.9d).
  - Complete treatment observation (see Section 4.5) if patient refuses further treatment or if clinician determines retreatment isn't feasible.
- 13.9b Patients who go off protocol treatment due to adverse events or DLT during initial treatment will go to observation (see Section 4.3). If PD occurs in observation, patients will go to event monitoring (see Section 4.4).
- 13.9c Patients who go off protocol treatment for reasons other than adverse events during initial treatment will go to the event-monitoring phase (see Section 4.4).
- 13.9d **Retreatment**
- Retreatment can be considered at any time when deemed clinically safe.
- DC created from the original leukopheresis must be available
  - Tumor lesion(s) must be amenable to cryoablation.

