### 16.322 Secondary Outcome Analyses:

These analyses will include all patients meeting the eligibility criteria who have signed a consent form and have begun treatment. Analyses will include all patients enrolled in the Phase II portion of the study and analysis of each cohort separately.

16.323 Complete response (Goal 2.2.21): The response rate will be calculated, as above, in each individual cohort as supplementary to the primary analysis.

16.324 Progression free survival, treatment free survival, and duration of response (Goal 2.2.22):

Survival time is defined as the time from registration to death due to any cause. The distribution of survival time will be estimated using the method of Kaplan-Meier (Kaplan E 1958). In addition, the overall survival rate at 2 years after registration will be reported.

Treatment free survival time is defined for all evaluable patients who have achieved a response as the time from registration to next treatment or death due to any cause. The distribution of treatment-free survival will be estimated using the method of Kaplan-Meier. In addition, the disease-free survival rate at 2 years after registration will be reported.

Duration of response is defined for all evaluable patients who have achieved a PR or CR as the date at which the patient's objective status is first noted to be a response to the earliest date progression is documented. The distribution of duration of complete response will be estimated using the method of Kaplan-Meier.

16.325 Adverse Events (Goal 2.2.23): All eligible patients that have initiated treatment will be considered evaluable for assessing adverse event rate(s). The maximum grade for each type of adverse event at each evaluation will be recorded for each patient, and frequency tables will be reviewed to determine patterns. Additionally, the relationship of the adverse event(s) to the study treatment will be taken into consideration. Longitudinal analysis techniques will be utilized to determine the effect

of time on treatment adverse events.

16.326 Quality of Life (Goal 2.2.24):

Quality of life as measured using the FACT-Lym will be utilized. The assessment will be scored according to the scoring algorithm. Changes from baseline will be calculated at each assessment time points. Mean change scores at each time point will be calculated to determine if quality of life is reduced over the course of treatment. Longitudinal techniques will be employed to describe changes over time.

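### Section 13.9c sends non-toxicity early stoppers to event monitoring, against 4.3, 4.4 and 13.31, and Section 13 has no branch for the early CR stops that 7.113 and 7.15 permit

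*Combined protocol and SAP*

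**What the plan says.** Section 13 routes patients by why initial treatment ended.

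- Toxicity, 13.9b: "Patients who go off protocol treatment due to adverse events or DLT during initial treatment will go to observation (see Section 4.3".
- Any other reason, 13.9c: "Patients who go off protocol treatment for reasons other than adverse events during initial treatment will go to the event-monitoring phase (see Section 4.4".
- Patients in response or stable, 13.31, under this condition: "If the patient has achieved CR, PR, or SD in initial treatment or optional pembrolizumab cycles, not requiring non-protocol alternative treatment". Observation visits then fall at 8 weeks from the last dose and every 3 months for a year, then less often until 4 years after registration.

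The schedules carry their own population statements. The title of 4.3 reads "Test Schedule for Observation for patients who do not complete initial active treatment for any reason or do not have dendritic cells for retreatment". Its table has exam, laboratory tests, AE assessment and CT or PET/CT every 3 months for 1 year. The title of 4.4 describes patients who refuse further treatment or observation, and its table has one row, the Event Monitoring form. The note under 4.1 allows 4.3 or 4.4 for any stop before Cycle 18 and refers back to Section 13.

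Section 7.113 permits early stopping in complete response: "Patients who achieved CR before Cycle 5 will complete treatments through cycle 6 and can then stop treatment at the discretion". The decision is left to provider and investigators jointly. Section 7.15 repeats this. A CR reached at or after Cycle 5 may lead to a stop after two more cycles.

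Section 16.324 measures duration of response up to the first documented progression, and adds: "In addition, the disease-free survival rate at 2 years after registration will be reported".

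**The concern.** The same patient can be put on two different follow-up schedules, depending on which sentence the site reads. Other sections already route starts of non-protocol therapy (13.1), progression (13.5, 13.6) and toxicity (13.9b). What remains for 13.9c is therefore largely patients who have not progressed, and a CR patient who stops early as permitted is the clearest case.

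If 13.9c governs, these patients lose scheduled imaging and AE assessment, while patients who stop for toxicity keep both. Intensity of surveillance then depends on the reason for stopping. PFS and duration of response, both secondary goals in 2.222, depend on when progression is found. Without a scan schedule, progression tends to be dated later and less exactly, which lengthens the apparent response. AE assessment matters too, because 8.2 notes that pembrolizumab events can appear months after the last dose.

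**Working it through.** The plan states no figure on this point to reproduce. The check sets the passages side by side and then works out a timeline.

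**Routing.** Take a patient in CR at the Cycle 4 scan (4.1, note 9) who stops after Cycle 6.

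| Provision | Where it sends this patient | Scheduled scans and AE assessment |
|---|---|---|
| 13.2 | Not covered: assumes 18 cycles | n/a |
| 13.9b | Not covered: AE or DLT only | n/a |
| 13.9c | Event monitoring, 4.4 | None in the table |
| Title of 4.3 | Observation, 4.3 | Every 3 months for 1 year |
| Title of 4.4 | Not event monitoring, unless the patient refuses | n/a |
| 13.31 | Treatment Observation, 4.5 (DC available) | Every 3 months for 1 year, from 4.5 |
| Note under 4.1 | 4.3 or 4.4, as Section 13 decides | Undetermined |

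Three destinations are possible and nothing in the text ranks them. Section 13.6 adds a further mismatch: it sends patients to observation but cites 4.4, which is event monitoring.

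**Timeline on the scanned routes.** Inputs:

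- A cycle is 21 days and a month is 28 days (7.111, notes to 4.1).
- Observation starts 56 days after the last dose, or at Week 62 if that is earlier (4.3, 4.5).
- Scans then run for 1 year (4.3, 4.5, 11.1), taken as 12 × 28 = 336 days or as 365 days.
- The landmark is 2 years from registration, day 730.
- Assumption: Cycle 1 Day 1 is the day of registration.

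For a last dose at Cycle k: last dose day L = 1 + 21 × (k − 1); start S = L + 56; end of scans = S + 336 to S + 365; shortfall = 730 − end.

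| Last cycle | L | S | End of scheduled scans | Days short of 730 |
|---|---|---|---|---|
| 6 | 106 | 162 | 498–527 | 203–232 |
| 8 | 148 | 204 | 540–569 | 161–190 |
| 12 | 232 | 288 | 624–653 | 77–106 |
| 18 | 358 | 414 | 750–779 | none |

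Week 62 ends on day 62 × 7 = 434, after day 414, so that cap does not bind. Section 6.36 lets treatment start up to 21 days after registration. At the full lag the Cycle 6 shortfall is 182–211 days.

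The later column of 4.5, headed "Every 4 months during second year post treatment, every 6 months thereafter until 4 yr post registration", marks only the Event Monitoring form. The shortfall at 2 years therefore arises on every route for early stoppers and is not caused by 13.9c.

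**The case against.** The strongest reply is that a stop permitted by 7.113 counts as completing treatment, not as going off it. Then 13.9c never applies, and 13.2 and 13.31 lead to observation. The 8-weeks-after-last-dose start would fit that. The reading is possible, but the note under 4.1 treats every stop before Cycle 18 as one class and offers only 4.3 or 4.4, so the text does not settle it. Section 13 also refers to a Patient Map that is not in the documents. It may resolve the routing in practice, but the protocol text would still conflict.

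Other objections stand and limit the point:

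- A reader might infer that response duration goes unmeasured in these patients. It does not. Section 4.4 collects status every 3, then 4, then 6 months until progression, with supporting documentation, and 18.5 requires imaging reports for patients who progress. What is lost is scheduled imaging and precision of dating.
- The last column of 4.3 and of 4.5 mentions assessment before entry to event monitoring and marks imaging. It can be read as requiring one scan at that point, though not a series.
- A reader might take 13.9c to catch every patient who stops for a non-toxicity reason. Sections 13.1, 13.5 and 13.6 route some of them separately.
- Section 13.31 does not itself mention scans. They come from 4.3, 4.5 and 11.1.
- A reader might suppose that early CR stoppers make up a large share of responders. The target ORR gives 0.53 × 28 = 14.8 responders, but that counts CR and PR together. The plan gives neither a CR rate nor an early-stop rate, and stopping is discretionary.

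**Conclusion.** The contradiction is real and should be fixed. Section 13.9c cannot be followed together with the titles of 4.3 and 4.4, and Section 13 has no explicit branch for permitted early CR stops. Followed literally, it leaves non-progressing patients without a series of protocol-scheduled scans or AE assessments, and progression dates for PFS and duration of response then come from unscheduled local imaging. That consequence assumes that sites apply 13.9c to a 7.113 stop, which the text allows but does not compel.

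The effect is confined to secondary endpoints and follow-up safety data. The primary endpoint is objective status during therapy (16.3211) and is not touched. The number of patients affected cannot be estimated from the documents.

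The missing 2-year imaging is a separate and smaller matter. It is tempting to attribute it to 13.9c, but it follows from the 1-year limit on observation scans stated in 11.1, and a last dose at Cycle 6 leaves about 200 to 230 days uncovered even under 4.3 or 4.5. How far this matters also depends on what disease-free means. Section 16.324 leaves the term undefined, in a paragraph whose events are next treatment or death.

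**What to change.** 1. Reconcile 13.9c with 4.3, 4.4, 13.31 and the note under 4.1. Event monitoring would cover the patients that the title of 4.4 and Sections 13.1 and 13.5 describe. Other patients who stop initial treatment without progression would follow the observation assessments already in 4.3 or 4.5. Separate explicit routes to event monitoring, such as 13.8 and 13.9e to 13.9g, are not part of this change.
2. Add a follow-up branch that names CR stops under 7.113 and 7.15. Eligibility for retreatment is left to the sponsor.
3. Make the destination and the section number in 13.6 agree.
4. State in 16.324 that, for early stoppers, the 2-year disease-free rate is not based on scheduled scans.

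The cost is wording in Section 13, the notes to Section 4 and one sentence in 16.324. No assessment is added beyond those in 4.3 and 4.5, although patients who would otherwise have gone to 4.4 will attend those visits.

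Longer imaging is not needed for this correction. Nor is a rule that censors everyone at the last scan advisable: patients still in event monitoring would contribute clinically detected progressions as events but little event-free time, which would bias the Kaplan-Meier estimates downward.

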## 14.0 Body Fluid Biospecimens

### 14.1 Summary Table of Research Blood/Blood Products to Be Collected for This Protocol

Collect and process all blood/blood products according to instructions and table below. For immunological monitoring Panels 1, 2, 3 and 4 will be collected.

#### 14.11 Collection During Treatment

Correlative Study (Section for more information)	Mandatory or Optional	Blood or Body Fluid being Collected	Component being harvested	Type of Collection Tube (color of tube top)	Volume to collect per tube (# of tubes to be collected)	Day 1 of designated cycles 	Process at site? (Yes or No)	Temperature Conditions for Storage/ Shipping 
Immune Monitoring Panel 1 (14.3)	Mandatory	Whole Blood	Plasma, Cells for DNA/RNA, Protein, and immunologic assays	EDTA (purple)	6 mL (1) 10 mL (2)	X	No	Room temperature
Immune Monitoring Panel 2 (14.3)	Mandatory	Whole Blood	Plasma, Cells for DNA/RNA, Protein, and immunologic assays	Heparin (green)	10 mL (4) 6 mL (1)	X	No	Room temperature
Immune Monitoring Panel 3 (14.3)	Mandatory	Whole Blood	DNA/RNA/Protein assays	Streck Cell Free DNA BCT	10 mL (1)	X	No	Room temperature
Immune Monitoring Panel 4 (14.2)	Mandatory	Whole Blood	serum	Serum Separator Tube (red tiger)	10 mL (1)	X	No	Room temperature

1. Cycle 1 order: blood for immune monitoring, leukapheresis, and MK-3475 administration. Order after Cycle 1: blood for immune monitoring, Pembrolizumab.
2. Phase I dose level 1: Cycles 1, 2, 4, 6, 8, 12, 18. Phase I dose level -1: Cycles 1, 2, 4, 8, 12, 18. Phase II will follow the schedule of phase I dose level 1.
3. All specimens should be sent to [name], Human Cell Therapy Lab, Mayo Clinic, [name].

## 14.12 Blood Collection During Observation

Correlative Study (Section for more information)	Mandatory or Optional	Blood or Body Fluid being Collected	Component being harvested	Type of Collection Tube (color of tube top)	Volume to collect per tube (# of tubes to be collected)	Documented PD requiring active treatment at any time during treatment or observation, prior to entering event monitoring, at End of Observation	Day 1 of Cycles 19-22 Every 3 months for 1 year (start at 8 weeks after last dose)	Process at site? (Yes or No)	Temperature Conditions for Storage /Shipping
Immune Monitoring Panel 1 (14.2)	Mandatory	Whole Blood	Plasma Cells for DNA/RNA, Protein, and immunologic assays	EDTA (purple)	6 mL (1) 10 mL (2)	X	X	No	Room temperature
Immune Monitoring Panel 2 (14.2)	Mandatory	Whole Blood	Plasma Cells for DNA/RNA, Protein, and immunologic assays	Heparin (green)	10 mL (4) 6 mL (1)	X	X	No	Room temperature
Immune Monitoring Panel 3 (14.3)	Mandatory	Whole Blood	DNA/RNA/Protein assays	Streck Cell Free DNA BCT	10 mL (1)	X	X	No	Room temperature
Immune Monitoring Panel 4 (14.2)	Mandatory	Whole Blood	serum	Serum Separator Tube	10 mL (1)	X	X	No	Room temperature

1. All specimens should be sent to [name], Human Cell Therapy Lab, Mayo Clinic, [name]

## 14.2 Background/Methodology

### 14.21 In vitro functional studies

In all cases, we will select CD3+ cells from the remainder of the cells found in the leukapheresis. These and T cells collected from subsequent time points can be in assessment of T cell functions including proliferation, cytokine production, response to Pevnar and DC stimulation and T cell receptor gene sequencing. In addition, we will keep samples of mDC from each patient and use these cells to stimulate peripheral blood collected as per the test schedule and assay for anti-tumor response via proliferation, ELISpot, or intracellular cytokine expression. A change above two times baseline control or more than 30% from assay prior to treatment will be considered significant response.

### 14.22 Immune phenotyping

We will immune phenotype blood for circulating Tregs, central memory and effector memory T cells, quantitative T, B, and NK cell panel, dendritic cells and immune suppressor cells (CD14+DRneg) and other immune modulating cells per our prior experience. PD-1, PD-L1 and PD-L2 expression on leukocyte subset will be analyzed. We will also collect and store plasma, serum and may collect white blood cells for future protein, RNA or DNA analysis. In particular, based on our preclinical studies, for patients with abnormally high percentage of CD14+HLA-DRlow/neg monocytes prior to treatment, a change greater than 10% in the percentage of these cells after treatment would be considered a statistically significant change.

